## INTRODUCTION AND OVERVIEW OF THE STATISTICAL ANALYSIS PLAN (SAP)

The Chronic Obstructive Pulmonary Disease (COPD) Biomarkers Qualification Consortium (CBQC) was established to combine the expertise of representatives from industry, academia, and the government with the goal of improving the time to development of new medications used to treat COPD. CBQC is interested in identifying biomarkers such as fibrinogen that could be used to enrich clinical trial populations with patients at increased risk of clinically important COPD outcomes. To this end, the CBQC Fibrinogen working group collaborated with academic leaders and contracted with INC Research to create an integrated database comprising 6 studies that collected plasma fibrinogen, a potential biomarker of COPD exacerbations and mortality, in patients with COPD. Evidera was asked to analyze this integrated database for the purpose of supporting the qualification of plasma fibrinogen as a biomarker for COPD to enrich the study populations for future clinical trials.

The main purpose of the SAP is to describe retrospective data analyses to assess the relationship between plasma fibrinogen and hospitalized COPD exacerbations and mortality. The SAP will guide the analyses performed and the content will be developed in collaboration with the CBQC with input from academic experts and the FDA.

### Background

Several studies have demonstrated that plasma fibrinogen concentrations are higher in COPD populations when compared to healthy controls after adjusting for key determinants that independently impact plasma fibrinogen concentration such as age, gender, and smoking (Duvoix et al., 2012; Dahl et al., 2001).

There have been reports from studies of the general population and COPD subjects measuring the relation between plasma fibrinogen and clinical COPD outcomes, including exacerbations and mortality. These studies have recently been reviewed by Duvoix et al. (2012) and will be briefly summarized here. In the Copenhagen City Heart Study, an adult Danish general population study (Dahl et al., 2001) reported that over a 6-year follow up period the risk for COPD hospitalization was highest for subjects with the highest plasma fibrinogen concentrations. In the COSMIC (COPD and Seretide: a Multi-Center Intervention and Characterization) study, a one-year prospective study in COPD patients, Groenewegen et al. (2008) reported that COPD subjects (with 2 or more exacerbations in the year prior to enrollment) experiencing exacerbations requiring treatment with oral steroids or exacerbations requiring hospitalization had higher plasma fibrinogen concentrations at baseline than did subjects who did not exacerbate. There was a rate ratio of 1.19 for each g/L increase in plasma fibrinogen for moderate exacerbations and a hazard ratio increase of 1.77 for severe exacerbations. In a population-based retrospective study in Sweden, Engstrom et al. (2009) reported that for each 0.8 g/L increase in plasma fibrinogen, a risk-adjusted 1.25 increase in the hazard ratio for COPD hospitalizations was observed.

In a meta-analysis of 31 individual studies, the Fibrinogen Studies Collaboration investigators (2005) assessed the relationship between plasma fibrinogen concentration and risk of mortality from cardiovascular and non-cardiovascular causes. For COPD mortality, using a case-control design, each 1

g/L increase in plasma fibrinogen was associated with a hazard ratio for mortality of 4.5 in the first 5 years of follow-up.

In an analysis combining subjects from the ARIC and CHS studies, Valvi et al. (2012) reported that mean plasma fibrinogen concentrations increased with increasing severity of COPD. Subjects whose plasma fibrinogen concentration was in the top decile for the cohort (>393.0 mg/dL) were at increased risk for COPD-related hospitalizations and death during follow-up (mean follow-up time of 9.7 years). This relation remained even after adjusting for potential confounders such as CVD (self-reported), age, gender, race, smoking status, and BMI. Mannino et al. (2012) recently reported the results of an analysis of participants in the NHANES III study. Participants with COPD, particularly GOLD stage defined stages 3 and 4 had higher plasma fibrinogen concentrations when compared to subjects with milder COPD or non-COPD subjects. Elevated plasma fibrinogen was associated with an increased risk for all-cause mortality. Information on COPD exacerbations/hospitalizations was not reported.

Although this prior research provides evidence of the association between high fibrinogen and COPD exacerbations, published literature is not currently available that would support the use of fibrinogen as a biomarker for increased risk of COPD-related outcomes during a time period that would be relevant to the conduct of a clinical trial. Moreover, the integration of 5 independently conducted studies will provide evidence regarding the robustness of fibrinogen as a biomarker of adverse COPD outcomes across various patient populations and time periods.

**These data present considerable evidence that plasma fibrinogen is closely related to COPD and COPD exacerbations, and support a formal quantitative assessment of plasma fibrinogen as an independent predictor of clinical endpoints in patients with COPD.**

## Objectives

The specific objectives for this analysis are to:

1. Verify the integrity of the integrated database
2. Describe the demographic and clinical characteristics of patients in the integrated database
3. Evaluate methods of defining patients with COPD
4. Assess longitudinal variation in plasma fibrinogen between individuals and within individuals
5. Define a cut point for classifying patients as having high fibrinogen levels
6. Assess the relationship between fibrinogen and risk of mortality and hospitalized COPD exacerbations during relevant time windows

## General Statistical Considerations

This is a retrospective database analysis of previously collected data from prospective clinical trials and observational studies. These data offer an opportunity to evaluate the relationship between plasma fibrinogen and adverse COPD outcomes by pooling data from multiple sources. Analyses will be conducted separately for individual studies and integrated as indicated. Data will be pooled across the

data sources as deemed appropriate for the analysis being conducted to uphold model assumptions and per variables available within each study.

Adverse COPD outcomes that will be assessed in these analyses include COPD exacerbations and all-cause mortality. The primary endpoint of clinical trials for COPD medications is a hospitalized COPD exacerbation; however, all-cause mortality does hold clinical importance in both the conduct of clinical trials and the overall management of any chronic disease.

As the data are analyzed, some deviation from the analyses outlined is anticipated (e.g., due to missing data; small sample sizes). In instances where these deviations would make the proposed analyses inappropriate, modifications to the analysis plan will be made in consultation with the CBQC and noted in the final report.

SAS statistical software version 9.2 (SAS Institute Inc., Cary, NC) will be used to conduct the analyses. All statistical tests will be two-sided and use a significance level of 0.05 unless otherwise noted. No adjustments for multiple comparisons will be performed unless otherwise noted. For all analyses, missing data will be considered randomly missing, and no data imputations or other algorithms for missing responses will be performed unless otherwise indicated. For certain procedures (such as analysis of variance) subjects with missing data will be excluded from the analysis.

### Currently Available Data

The currently available data includes the following studies:

1. Atherosclerosis Risk in Communities (ARIC) study: A US general population-based study begun in 1987 (The ARIC Investigators, 1989). The study recruited 15,792 participants in four communities: Forsyth County, NC; Minneapolis, MN; [name]; and Jackson, MS. Plasma fibrinogen and spirometry (non-bronchodilator) were collected at baseline.
2. Cardiovascular Health Study (CHS): A general population-based study of US participants aged 65 years and older (Fried et al., 1991). The study was initiated in 1988. The original CHS cohort comprised 5201 subjects recruited from four communities: Forsyth County, NC; Pittsburgh, PA; Sacramento County, CA; and [name]. Plasma fibrinogen and spirometry (non-bronchodilator) were assessed at the baseline visit.
3. Evaluation of COPD Longitudinally to Identify Predictive Surrogate End-points (ECLIPSE): A 3-year prospective, observational study conducted in 46 sites in 12 countries (Vestbo et al., ERJ). The ECLIPSE cohort included 2164 COPD subjects with moderate to very severe COPD (GOLD stages II, III, and IV) along with smoking and non-smoking control groups (Agusti et al., 2010). Only the COPD subjects will be included in the proposed analysis. Plasma fibrinogen was measured at baseline and longitudinally during the 3 years of ECLIPSE.
4. Framingham Heart Study (FHS) Offspring Cohort: A non-randomized cohort study initiated in 1971 (Kannel et al., 1979). Over the ensuing decades, several follow-up examinations were conducted. The cohort initially consisted of 5124 subjects (all subjects were offspring or spouses of offspring of participants in the original Framingham Heart Study). Plasma fibrinogen and

pre-bronchodilator spirometry were collected beginning with exam visit 5 of the offspring cohort study with follow-up hospitalization and vital status information available for a 25-year period. In contrast to several of the other studies proposed for inclusion, longitudinal measurements of plasma fibrinogen and lung function are available from two subsequent exam visits.

5. National Health and Nutrition Examination Survey (NHANES) III: A general population-based cross-sectional study of a representative sample of the US population. Plasma fibrinogen concentration and spirometry (pre-bronchodilator) are available from 8342 adults aged 40 years and above.

#### Supplemental data:

COPDGene: A prospective cohort study conducted at 21 sites in the United States. The COPDGene cohort includes 4,000 smoker controls with normal spirometry measurements (FEV1/FVC ratio  $\geq 0.7$ , FEV1  $\geq 80\%$  predicted), 2,000 patients meeting the criteria for GOLD stage 1 and GOLD stage unclassified (GOLD-U), 4,000 patients meeting the criteria for GOLD stages 2–4, and 100 non-smoker controls, for a total enrollment of 10,100 patients. Plasma fibrinogen was not collected in this study; therefore, data from this study will be used only to compare the diagnosis of patients using pre- and post-bronchodilator spirometry measurements, which were collected in the study.

Table 1. Study Population Information for Studies Proposed for Inclusion

Study	Study Population (n)	COPD Subjects (n)*	Longitudinal Fibrinogen Availability	Hospitalized COPD Exacerbations Within 12 months	Deaths within 3 Years among COPD Subjects
ARIC	15,462	1,789	No	96	86
CHS	5,730	1,292	No	236	120
ECLIPSE	2,726	2,118	Yes	335	220
Framingham Offspring Cohort	3,885	145	No	N/A	13
NHANES III	1,369	1,032	No	N/A	146

\* Aged ≥40 years and GOLD Stages 2, 3, or 4 – based on pre-bronchodilator spirometry

ARIC = Atherosclerosis Risk in Communities Study; CHS = Cardiovascular Health Study; COPD = chronic obstructive pulmonary disease; ECLIPSE = Evaluation of COPD Longitudinally to Identify Predictive Surrogate Endpoints; FHS = Framingham Heart Study; NHANES = National Health and Nutrition Examination Survey

Studies have been evaluated and integrated into one database for these analyses. Analyses described here will be conducted using both the individual study datasets and the full integrated dataset.

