## Outcome Ascertainment

Exacerbations and other clinical events were recorded differently in each study depending on the study objectives and population. In ARIC and CHS, exacerbations were identified as hospitalizations with an International Classification of Diseases, 9th Revision, Clinical Modification (ICD-9-CM) code of (490.x, 491.x, 492.x and 496.x) in any position (principal or supporting diagnosis). In ECLIPSE, hospitalized COPD exacerbations were recorded in the supplemental clinical event file as 'EXACHOSP'. COPD exacerbations were not recorded outcomes in NHANES or FHS. All-cause mortality was recorded in each study in the integrated database.

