## Assay Methods

Several laboratory methods are available for the determination of plasma fibrinogen and these can be classified into two general categories:

1. *Functional methods* that measure "clottable" fibrinogen (Clauss method)
2. *Direct methods* that quantify the fibrinogen protein (Immunologic method)

In routine clinical laboratory practice, plasma fibrinogen is most commonly measured by a functional method that determines thrombin-clottable protein in plasma samples derived from whole blood collected with sodium citrate as the anticoagulant. These methods are based on the original method of Clauss and are frequently referred to as the Clauss or modified Clauss methods (Kamath and Lip, 2003). Direct methods, primarily methods that measure immunoreactive fibrinogen protein, are also available, and several have been developed for use with clinical samples. The immunologic methods have the advantage that they can be used with plasma prepared with a variety of anticoagulants (e.g., sodium citrate, EDTA), whereas the functional assays are most appropriately limited to plasma samples prepared with anticoagulants that have no impact on clottable fibrinogen, e.g., sodium citrate. Both the functional-based and immunologic-based methods can be calibrated against accepted international standards allowing for results from different laboratories, different methods, or different testing occasions to be properly compared (Whitton et al., 2000; Raut and Hubbard, 2010). For clinical studies, plasma fibrinogen concentration is typically measured in laboratories that adhere to accepted practices for the handling and testing of clinical samples and have well established and documented quality control processes for determining and monitoring assay performance. These assay methods were the subject of a literature review that was performed concurrently with these analyses.

Unpublished analyses have been conducted by industry to directly compare the fibrinogen results of samples tested using both the functional and direct assay methods, in order to identify an appropriate adjustment factor to account for the differences in fibrinogen results between these methods. Fibrinogen values for ECLIPSE have been corrected by -13.6% to account for the use of EDTA plasma instead of citrate plasma, based on data provided by the manufacturer of the assay used in ECLIPSE (Pacific Biometrics Inc., 2007).

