### Proposed Analyses

1. Assess the time-varying relationship between high fibrinogen and the risk of adverse COPD outcomes.

*Analysis:*

Cox proportional hazards models will be used to identify hazard risk ratios with corresponding 95% confidence intervals associated with fibrinogen levels as well as demographic and clinical characteristics. These models will account for the time-varying nature of the relationship between fibrinogen levels and exacerbations/all-cause mortality; as such, they can only be performed in studies that recorded the dates of outcomes of interest. There will be two main groups considered in the modeling process:

1. Age 40+, GOLD stage 2+, history of exacerbations unspecified
2. Age 40+, GOLD stage 2+, and any prior COPD exacerbation (ECLIPSE)

Analyses using hospitalized exacerbations as an endpoint will be completed for outcomes which are recorded within 12 months of the initial fibrinogen measurement. Analyses with mortality will be completed for outcomes which are recorded within 3 years of the initial fibrinogen measurement. Analyses will be conducted using the fibrinogen thresholds determined previously (250 mg/dL, 300 mg/dL, 350 mg/dL, and 400 mg/dL).

Each outcome model will be constructed as follows:

1. The association between baseline characteristics and each outcome will be examined using univariate models. These models will be fitted on data of patients with high and low fibrinogen, and will result in a set of baseline characteristics that are predictive of the outcome and will be used as candidates for the final model.
2. To identify confounders of the cohort-outcome effect (e.g., the association between high vs. low fibrinogen and a given outcome), all baseline characteristics will be tested individually in a model with cohort as the only other independent variable. Those variables modifying the cohort-outcome effect size by at least 10% will create an additional set of candidates for the final model.
3. To obtain the fully adjusted model, the first step will be to add the candidate variables from step 2 to the unadjusted model one at a time, in descending order of strength of the confounder (i.e., the percentage change in the hazard ratio that results from adding that variable to the unadjusted model). Variables that still modify the cohort-outcome effect size by at least 10% will be retained, as will any that are significant predictors of the outcome at  $P < 0.05$ .

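### Cox models on the integrated dataset have no stratum or term for source study, so the pooled fibrinogen hazard ratio can be biased in either direction

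*SAP*

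**What the plan says.** - **Analysis sets.** Below Table 1, the SAP says "Analyses described here will be conducted using both the individual study datasets and the full integrated dataset". General Statistical Considerations allows pooling across "sources as deemed appropriate for the analysis being conducted to uphold model assumptions and per variables available within each study". It names no test of heterogeneity and no model term for study.
- **Model.** In the section on fibrinogen and adverse outcomes, Proposed Analyses item 1, "Cox proportional hazards models will be used to identify hazard risk ratios with corresponding 95% confidence intervals associated with fibrinogen levels". The inputs are "fibrinogen levels as well as demographic and clinical characteristics". Five steps follow: univariate screening, a 10% change-in-estimate rule, retention of confounders and predictors, backward selection, and a correlation check. Source study is not in the variable lists of Descriptive Analyses 1.1 and 1.2, and it appears nowhere as a stratum, covariate or random effect.
- **The word cohort.** One step says that "all baseline characteristics will be tested individually in a model with cohort as the only other independent variable". Cohort here is not the source study: the SAP explains the cohort effect as "the association between high vs. low fibrinogen and a given outcome".
- **Differences between studies.** Outcome Ascertainment says "Exacerbations and other clinical events were recorded differently in each study depending on the study objectives and population": ICD-9-CM codes in any position in ARIC and CHS, and a study event file in ECLIPSE. Assay Methods says "Fibrinogen values for ECLIPSE have been corrected by -13.6% to account for the use of EDTA plasma instead of citrate plasma". Fibrinogen Classification applies the same four cut-points (250, 300, 350 and 400 mg/dL) to every study.
- **Later use.** The last Proposed Analyses item takes survival estimates from the Cox models to size a hypothetical trial.

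**The concern.** An unstratified Cox model gives all studies one baseline hazard. If study is related both to the outcome and to being above the cut-point, the fibrinogen coefficient absorbs part of the difference between studies. Table 1 shows that study is related to outcome. The SAP does not show whether it is related to fibrinogen group, but the populations (general-population cohorts and a recruited COPD cohort) and the assay handling make this plausible.

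At stake are the pooled hazard ratio, offered towards qualification of fibrinogen as an enrichment biomarker, and the sample sizes derived from the same models. The pooled Kaplan-Meier plots and the pooled comparisons of fibrinogen distribution by outcome have the same weakness. The second modelling group (prior exacerbation) uses ECLIPSE alone and is not affected.

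**Working it through.** The SAP gives no pooled hazard ratio and no sample size, so there is no figure of its own to reproduce.

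**1. Risk by study (Table 1).** Exacerbations were recorded in only three of the five studies. The column heading does not say whether it counts patients or events, or COPD subjects only; patients among COPD subjects are assumed.

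| Study | COPD n | Exacerbations, 12 months | Deaths, 3 years |
|---|---|---|---|
| ARIC | 1,789 | 96 (5.4%) | 86 (4.8%) |
| CHS | 1,292 | 236 (18.3%) | 120 (9.3%) |
| ECLIPSE | 2,118 | 335 (15.8%) | 220 (10.4%) |
| FHS | 145 | not recorded | 13 (9.0%) |
| NHANES III | 1,032 | not recorded | 146 (14.1%) |

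Highest over lowest is 18.3/5.4 = 3.4 for exacerbations and 14.1/4.8 = 2.9 for deaths. Chi-square for heterogeneity is 140.2 on 2 df and 75.3 on 4 df.

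**2. Pooled hazard ratio with no effect inside any study.** The shares above the cut-point are assumptions. At ARIC/CHS/ECLIPSE shares of 20/30/60%:

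- High group: n = 0.2×1,789 + 0.3×1,292 + 0.6×2,118 = 2,016.2; events = 0.2×96 + 0.3×236 + 0.6×335 = 291.0; risk 14.43%.
- Low group: n = 5,199 − 2,016.2 = 3,182.8; events = 667 − 291.0 = 376.0; risk 11.81%.
- Cumulative hazards, −ln(1 − risk): 0.1559 and 0.1257. Ratio 1.24.

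Solving the expected Cox score equation, with exponential hazards matched to the Table 1 risks, also gives 1.24 (95% CI 1.06-1.44).

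At 50/30/30% the groups have 219.3/1,917.5 = 11.44% and 447.7/3,281.5 = 13.64%. The cumulative hazards are 0.1215 and 0.1467, ratio 0.83 (Cox 95% CI 0.70-0.97).

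**3. Other assumed shares, exacerbations, Cox solution.**

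| ARIC/CHS/ECLIPSE share | Pooled, true HR 1.00 | Pooled, true HR 1.50 |
|---|---|---|
| 30/30/30% | 1.00 | 1.49 |
| 25/35/40% | 1.12 (0.96-1.32) | 1.67 |
| 20/40/40% | 1.21 (1.03-1.41) | 1.79 |
| 20/40/60% | 1.29 (1.11-1.51) | 1.86 |
| 50/30/30% | 0.83 (0.70-0.97) | 1.22 |

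Stratified by study, every row returns 1.00 and 1.50. Over shares of 15-40% (ARIC), 30-50% (CHS) and 50-70% (ECLIPSE), the unstratified null value runs from about 1.00 (40/30/50%) to 1.47 (15/50/70%).

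**4. Mortality, five studies.** Over the same shares, with FHS and NHANES III set equal to CHS, the null pooled hazard ratio is about 0.98 to 1.26. With shares of 50/40/30/30/30% (ARIC/CHS/ECLIPSE/FHS/NHANES III) it is 0.89.

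**5. Hypothetical trial.** For a hazard ratio of 0.7, 80% power and two-sided 0.05, events = 4(1.960 + 0.842)²/(ln 0.7)² = 247.

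- ARIC risk: control 5.37%, treated 1 − (1 − 0.0537)^0.7 = 3.79%, mean 4.58%. 247/0.0458/0.9 is about 6,000 patients.
- CHS risk: 18.27% and 13.17%, mean 15.72%. 247/0.1572/0.9 is about 1,750 patients.

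The mix of studies behind a pooled baseline hazard therefore drives this output too.

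**6. Assay.** A cut at 350 mg/dL on corrected ECLIPSE values is 350/(1 − 0.136) = 405 mg/dL as measured. The cuts at 250, 300 and 400 are 289, 347 and 463.

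**The case against.** The best defence is that every study is also analysed alone. Those estimates are free of between-study confounding, and study-specific hazard ratios with confidence intervals are already planned. The SAP pools only where judged appropriate, presents pooling as evidence of robustness across populations, and nowhere makes the pooled estimate the sole evidence. This stands and limits the harm. It does not repair the pooled hazard ratio, and no rule says how the study results qualify it.

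It is also fair that the calculations above are unadjusted, while the planned models may retain age, FEV1 or smoking. Those could absorb some case mix. They are not guaranteed to survive selection, and they do not correct differences in outcome coding or assay.

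A reader might infer that differences between studies will appear as a harmful fibrinogen effect, so that the pooled hazard ratio is inflated. The SAP does not support that. It gives no share above any cut-point by study; equal shares give no bias under the null, and some patterns push the estimate below 1. The downward ECLIPSE correction itself lowers that study's share. A reader might also infer that stratification settles the assay question. It does not, because a mis-scaled cut-point misclassifies patients within ECLIPSE.

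**Conclusion.** The point holds as a gap in model specification. The SAP commits to pooled analyses, details the Cox build and leaves source study out, while its own table shows risks differing about threefold or more. The resulting bias is possible, not shown, and its sign is unknown. With no true effect, the pooled exacerbation hazard ratio is 1.00 at equal shares, 1.24 at 20/30/60% and 0.83 at 50/30/30%, so some plausible patterns would give a nominally significant result in either direction.

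These sizes rest on assumed shares, constant hazards within study, no covariate adjustment, and the stated reading of the exacerbation column. The omission itself and the mortality differences do not depend on those assumptions.

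**What to change.** In Proposed Analyses item 1:

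- State that every pooled Cox model is stratified by source study (STRATA in PROC PHREG), including the models used for variable screening.
- Report the fibrinogen-by-study interaction beside the study-specific hazard ratios already planned.
- Show the pooled Kaplan-Meier plots and the fibrinogen distribution comparisons by study. The SAP plans no log-rank test, so none needs changing.
- Base the hypothetical-trial sample sizes on study-specific baseline survival.

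Separately, add a sensitivity analysis with uncorrected ECLIPSE values or with within-study fibrinogen quantiles.

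None of this needs new data. The cost is a statement in the code, a few outputs and a small possible loss of precision. At 20/30/60% shares the log-scale 95% interval widens from ln(1.445/1.064) = 0.306 to ln(1.177/0.850) = 0.325, about 6%. The pooled hazard ratio may move up or down.
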